9.0 Study Endpoints

- 9.1 The primary endpoints in this study are as follows:
 - visual acuity
 - contact lens comfort questionnaire
 - keratograph surface evaluation (tear break up score)
 - ocular surface staining

Page 8 of 22 Revised: July 24, 2017

- 9.2 The secondary endpoints in this study are as follow:
 - contact lens fitting characteristics (apical clearance, limbal clearance, scleral landing evaluation)

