Questionnaires	Subjects will be asked to fill out the following questionnaires: • Contact Lens Dry Eye Questionnaire - 8 (CLDEQ - 8) • Visual analog scale (VAS) 0-100 • Secondary VAS scales at Visits 2-5 (unique to each visit) These questionnaires assess the level of eye and/or contact lens discomfort, and assess the subject perception of their habitual lenses and the coated lenses before and after Boost treatment.	No

Page 12 of 22 Revised: July 24, 2017

FULL PROTOCOL TITLE: An Evaluation of Tangible Boost Replenishing System on the Continued Efficacy of Tangible HydraPEG Rigid Gas Permeable Contact Lens Coating.

0.1.1/0.1	TT1 ' '11 ("1 1 1 1 1 1 1	NT
Scleral/Corneal lens fitting	The examiner will fit the subjects with scleral or corneal contact lenses using commercially available lens fitting sets (AVT scleral and corneal designs, AVT Technologies, CO). The lenses will be fit using the customary fitting procedure, where a diagnostic lens is applied to the eye, an over-refraction is performed, and then customized lenses are ordered with the over-refraction incorporated and any fitting parameters are altered based on the investigators' expertise. Once the lenses are dispensed, the subjects will be reminded of proper handling and cleaning techniques, and given a handout on lens care. In addition, at the 30-day visit subjects will be given instructions on the tangible boost kit or placebo that they are supplied.	No
Scleral/Corneal	The ordered rigid lenses will be applied to the eye of the	No
Lens Evaluation	subject by the investigator, after which the fit and vision will be evaluated. At this time, if the fit of the lens is adequate, the lenses will be dispensed. If there are additional parameter changes needed, they will be ordered at this time.	
Visual Acuity	The participant's vision in each eye will be measured with a high contrast visual acuity chart for the subjects' habitual lenses and the test lenses. The participant will be asked to cover one eye and read the chart, and this procedure will be repeated for the other eye.	No
Slit-lamp	The participant's front portion of each eye and contact	No
Examination	lenses will be examined with a lighted microscope. The participant will be asked to place his/her chin on the chinrest and place his/her forehead against the bar and look straight ahead. The instruments light will be shined onto the eye to visualize the ocular surface for approximately 2-3 minutes per eye.	

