24.0 FERPA - N/A

25.0 Data Management

25.1 Describe the data analysis plan, including any statistical procedures.

Data will be stored in a study paper file. Paper files will be kept in a filing cabinet within The Ocular Surface Institute (Health and Biomedical Sciences Building). Electronic data will be stored on a password-protected computer in a locked office in rooms 232, 236 or 250 within The Ocular Surface Institute of the Health Biological Sciences Building (HBSB). All study data will remain on UH property within The Ocular Surface Institute for a minimum of 3 years following study completion. The principal investigator will be

Page 20 of 22 Revised: July 24, 2017

responsible for maintaining study data security and subject confidentiality, and the PI and the study coordinator will be responsible for receipt and transmission of the data. The investigative team, study sponsor and inspectors from regulatory agencies such as the US Food and Drug Administration will have access to the data if requested for study monitoring or an audit.

All collected data will be documented on study documents and analyzed for differences between baseline and test data. Hypothesis testing will be performed using statistical analyses including parametric or nonparametric comparisons (i.e., t-tests, signed-rank tests), analysis of variance, general linear models, correlation, or regression techniques.

The recorded audio and video data will be sent to UserWise for analysis of the usability of the product.

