5.	Birthdate (mm/dd/yy):/				
6.	Gender: \square_1 Male \square_2 Female				
7.	Lens Indication:				
8.	Lens Type (circle one): Scleral	Corneal			
9.	Duration of lens wear (months/years):				
10.	Average # hours lens wear per week:				
11.	Hours of lens wear today:				
12.	CLDEQ-8 a. CLDEQ-8 completed and verified:	□₁ Yes	\square_2 No	CLDEQ-8 score:	
13.	VAS scale a. VAS scale completed and verified:	□ ₁ Yes	\square_2 No	VAS score:	
14.	Medications and Medical History a. Current medications or supplements?		□ ₁ Yes	\square_2 No	

UNIVERSITY of HOUSTON

15.

Diameter: ____ Lens Power:

Limbal Profile: _____

Landing Zone Profile: ______

Subject:	

_					
TH	IE OCULAR SURFACE INSTITUTE		Date:	/	/
	Evaluation of Tangible Boost F	Replenish	ing Syst	em	
c. d. e. f.	Was the concomitant medication log completed? Medical or ocular conditions? Was the medical and ocular history log completed? History of ocular surgeries, ocular injections or laser □₁ Yes □₂ No (If No, skip to question 10) Was the surgery more than 12 weeks ago? □₁ Yes Type of ocular surgery and when it occurred? /	\Box_1 Yes \Box_1 Yes procedures?	\square_2 No \square_2 No \square_3 N/A	ate:	/
Со	ntact lens history				
a.	Current lens brand				
00					
OS	·				
b.	Current lens parameters (if known)				
	Base curve:				
	SAG:				
	Diameter:				

c.	Did subject wear their own contact lenses 2 days prior to this appointment? \square_1 Yes \square_2	No

Visual Acuity with habitual lenses (logMAR): Record # of letters seen **16.**

OS: OD: _____

Over refraction (spherical only) **17.**

OD OS

Examiner Initials:

THE OCULAR SURFACE INSTITUTE

Sub	oject:		_
Date:	/	/	_

Evaluation of Tangible Boost Replenishing System

	OD			OS
		Movement		
		Centration		
		Apical Clearand	ce	
		Limbal Clearan	ce	
		Scleral Landing Z	one	
		Commonts		
Perform Kera	atograph NIBUT			
OD:	NIKf-BUT "until b	olink" (first break up)		
	NIKavg-BUT "unt	il blink" (average break up)		
	Level:			
	NIKf-BUT "25 sec	conds" (first break up)		
	NIKavg-BUT "25	seconds" (average break up))	
	Level:		7	
				
OS:	NIKf-BUT "until b	olink" (first break up)		
OS:	NIKf-BUT "until b NIKavg-BUT "unt	olink" (first break up) il blink" (average break up)		
OS:	NIKavg-BUT "unt	il blink" (average break up)		
OS:	NIKavg-BUT "unt Level:	il blink" (average break up) 		
OS:	NIKavg-BUT "unt Level:	il blink" (average break up) 		
OS:	NIKavg-BUT "unt Level: NIKf-BUT "25 sec	il blink" (average break up)		

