OS:	NIKavg-BUT "unt Level: NIKf-BUT "25 sec	il blink" (average break up) conds" (first break up) seconds" (average break up		
OS:	NIKavg-BUT "unt Level: NIKf-BUT "25 sec NIKavg-BUT "25 s	il blink" (average break up) conds" (first break up) seconds" (average break up		
	NIKavg-BUT "unt Level: NIKf-BUT "25 sec NIKavg-BUT "25 sec Level:	il blink" (average break up)		
	NIKavg-BUT "unt Level: NIKf-BUT "25 sec NIKavg-BUT "25 sec Level:	il blink" (average break up))	
	NIKavg-BUT "unt Level: NIKf-BUT "25 sec NIKavg-BUT "25 sec Level:	il blink" (average break up) conds" (first break up) seconds" (average break up val)		
	NIKavg-BUT "unt Level: NIKf-BUT "25 sec NIKavg-BUT "25 sec Level:	cil blink" (average break up) conds" (first break up) seconds" (average break up coval) Lids and lashes)	
	NIKavg-BUT "unt Level: NIKf-BUT "25 sec NIKavg-BUT "25 sec Level:	cil blink" (average break up) conds" (first break up) seconds" (average break up) oval) Lids and lashes Conjunctiva)	
	NIKavg-BUT "unt Level: NIKf-BUT "25 sec NIKavg-BUT "25 sec Level:	cil blink" (average break up) conds" (first break up) seconds" (average break up coval) Lids and lashes)	
	NIKavg-BUT "unt Level: NIKf-BUT "25 sec NIKavg-BUT "25 sec Level:	cil blink" (average break up) conds" (first break up) seconds" (average break up) oval) Lids and lashes Conjunctiva)	
	NIKavg-BUT "unt Level: NIKf-BUT "25 sec NIKavg-BUT "25 sec Level:	conds" (average break up) conds" (first break up) seconds" (average break up) coval) Lids and lashes Conjunctiva Sclera)	

THE OCULAR SURFACE INSTITUTE

Subject:	

Date:	/	/
Date.	, ,	,

Evaluation of Tangible Boost Replenishing System

_____ Lens

[figure not shown]
21. Eyelid Eversion (GPC grade level: Efron Scale, circle for each eye)

[figure not shown]
OD: Grade 0 Grade 1 Grade 2 Grade 3 Grade 4

OS: Grade 0 Grade 1 Grade 2 Grade 3 Grade 4

22. Corneal Fluorescein Staining:

(Efron Scale for each quadrant: 0-4 grading in each quadrant, total score range 0-20)

TOTAL Score: OD _____ OS ____

If subject is wearing scleral lenses, refit with diagnostics, if wearing corneal, order base curve and power based on their habitual lenses and any appreciative OR

23. Diagnostic Fitting with Study Lenses (Scleral Only):

a. Final Diagnostic Lens Parameters

Base curve: _____

Diameter:

Lens Power:

Limbal Profile:

Landing Zone Profile: ______

Subject: _		

Date:	/	′ ,	/

Evaluation of Tangible Boost Replenishing System

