*Note evalua 7.	: Habitual lens fit does not need to tion. Slit lamp exam (after lens remov OD	be re-evaluated at this (al) Lids and lashes Conjunctiva Sclera	visit. They ma	oy be removed without

[figure not shown]

Subject:	

Date: _____/_____

Evaluation of Tangible Boost Replenishing System

TOTAL Score: OD _____ OS ____

- 9. Fitting with Study Lenses:
 - a. Visual Acuity with Study Lenses (logMAR): Record # of letters seen

OD: _____ OS: OD: ____

b. Over refraction

OD _____

c. Slit Lamp Evaluation of Study Lenses
OD

Movement
Centration
Apical Clearance
Limbal Clearance
Scleral Landing Zone
Comments

10. Comments and suggested changes to lens parameters:

11. Need for New Lens order? \square_1 Yes \square_2 No \square_3 Maybe

Examiner Initials: _____

OS

TUC	\cap	AD C	SIIDEVOE	INSTITUTE
		AK	DUKLWCE	HINDHIULE

Subje	ect:		
Date:	/	/	

Base curv	e:	
Diameter	·	
Lens Pow	er:	
Limbal Pr	ofile:	
Landing Z	one Profile:	
13. Keratograph 14. Perform Kera	•	are dispensable)? \square_1 Yes \square_2 No
OD:	NIKavg-BUT "until blink" Level: NIKf-BUT "25 seconds" (first break up)s" (average break up)
OS:	NIKavg-BUT "until blink" Level: NIKf-BUT "25 seconds" (first break up)s" (average break up)
15. Contact lens	order form filled out? \Box_1	Yes \square_2 No \square_3 Not Applicable
16. Gift card give	n? \square_1 Yes	\square_2 No
17. Dispensed Le	nses? \square_1 Yes	\square_2 No

THE OCULAR SURFACE INSTITU	ΠH

Subject:		
Date:	_/	/

18. Dispensed Unique pH?	\square_1 Yes	\square_2 No			
19. Dispensed DMV?	\square_1 Yes	\square_2 No			
20. Dispensed PuriLens?	\square_1 Yes	\square_2 No			
21. Lens Dispense log filled out?	□ ₁ Yes	□ ₂ No			
22. Follow up appt made (30 days and +1 day)? \square_1 Yes \square_2 No					
23. Follow up appt dates: Appt 4 date:					
Appt!	5 date:				

Subject:		
Date:	_/	/

Evaluation of Tangible Boost Replenishing System

VISIT 3

ours of Rigid lens wear today:			
urrent Cleaning solution:			·
urrently wearing study lenses?	\square_1 Yes \square_2	No	
CLDEQ-8 a. CLDEQ-8 completed and verified	d: □₁ Yes	\square_2 No	CLDEQ-8 score:
'AS scale . VAS scale completed and verifie	ed: □₁ Yes	\square_2 No	VAS score:
o. Extended VAS scale completed:	\square_1 Yes \square_1 Yes \square_1 Yes \square_1 Yes	\square_2 No \square_2 No	removal: vision:
Medications a. Any changes in medications? b. If yes, please specify:	□ ₁		No
Visual Acuity with Study Lenses (lo	gMAR): Record # of	letters seen	
OD: OS:			

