8.	Visual Acuity with Study Lenses (logMAR):	Record # of le	tters seen			
	OD: OS:					
9.	Over refraction (spherical only) OD OS					

Subject:	 	

Date:	/	/

Evaluation of Tangible Boost Replenishing System

	OD		OS
			
		_	
		_ Comments	
erform Ker	atograph NIBUT		
OD:	NIKf-BUT "until l	olink" (first break up)	
	NIKavg-BUT "un	til blink" (average break up)	
	Level:		
	NIKf-BUT "25 se	conds" (first break up)	
	NIKavg-BUT "25	seconds" (average break up)	
	Level:		
0.5	NUMER DESTRUCTION	1: 17/75 . 1	
OS:		olink" (first break up)	
	Level:	til blink" (average break up)	
		1.11.75	
	NIKt-BUT "25 sec	conds" (first break up)	
		seconds" (average break up)	
	Level:		
lit lamp exa	ım (after lens remo	oval)	
lit lamp exa	nm (after lens remo	oval)	os
-	-	oval) _ Lids and lashes	os
-	OD		os
-	OD	Lids and lashes	OS
-	OD	Lids and lashes Conjunctiva	OS
-	OD	Lids and lashes Conjunctiva Sclera	OS
-	OD	Lids and lashes Conjunctiva Sclera Cornea	OS

[figure not shown]

Subject:		
=		

[figure not shown]
Date: _____/_____

Evaluation of Tangible Boost Replenishing System

13. Corneal Fluorescein Staining (0-4 grading)

TOTAL Score: OD _____ OS ____

14. Are lenses still adequate to be worn? \square_1 Yes \square_2 No

If no, please indicated parameter changes indicated below:

- **15. Gift card given?** \square_1 Yes \square_2 No
- **16. Dispensed Unique pH?** \Box_1 Yes \Box_2 No
- **17. Dispensed DMV?** \square_1 Yes \square_2 No
- **18. Dispensed PuriLens?** \square_1 Yes \square_2 No
- **19. Follow up appt made (60 days)?** \square_1 Yes \square_2 No
- **20.** Call-log filled out for **30** days (reminder)? \square_1 Yes \square_2 No
- 21. Follow up appt date: _____

THE	OCIII	ΔD	SURFA	CF	INISTII	HITE
		\sim IX	SUKEA	W-E	HINDIH	UIL

Subject:		
Date:	/	/

VISIT 5

1.	Time of Day (military time) ::			
2.	Hours of Rigid lens wear today:			
3.	Current Cleaning solution:			
4.	Currently wearing study lenses? \square_1 Yes	\square_2 N	lo	
5.	CLDEQ-8 a. CLDEQ-8 completed and verified:	□₁ Yes	□ ₂ No	CLDEQ-8 score:
6.	VAS scale a. VAS scale completed and verified:	□ ₁ Yes	\square_2 No	VAS score:
	b. Extended VAS scale completed:	\square_1 Yes \square_1 Yes	\square_2 No \square_2 No \square_2 No \square_2 No	removal: vision:
7.	Medications a. Any changes in medications? b. If yes, please specify:	□ ₁ Y		
8.	Visual Acuity with Study Lenses (logMAR)	: Record # of lo	etters seen	
	OD: OS:			
9.	Over refraction (spherical only) OD OS			

Subject	:		
Date:	/	/_	

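### A visual acuity gain from Visit 1 to the study lens can be a lens-power update, because the baseline visit is not named and habitual-lens acuity is scored before over-refraction

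*Combined protocol and SAP*

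**What the plan says.** Section 9.1 ("The primary endpoints in this study are as follows") lists visual acuity first of four. Section 10.2 has acuity measured in both the habitual and the test lenses.

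- **Visit 1 worksheet.** Item 16 reads "Visual Acuity with habitual lenses (logMAR): Record # of letters seen". Item 17 then records a spherical over-refraction for each eye. No acuity through that over-refraction is recorded.
- **Visit 2 worksheet.** Item 9a is "Visual Acuity with Study Lenses (logMAR): Record # of letters seen", and item 9b is the over-refraction. The Visit 3, 4 and 5 worksheets keep this order, with no acuity field after the over-refraction.
- **Ordering of the study lens.** In section 10.2 a diagnostic lens is applied, and then "an over-refraction is performed, and then customized lenses are ordered with the over-refraction incorporated". For corneal wearers the Visit 1 worksheet instead says to "order base curve and power based on their habitual lenses and any appreciative OR".
- **Existing wearers of the study brand (AVT).** Section 10.1 says that their parameters are simply re-ordered, although it also says that all lenses undergo a diagnostic fit.
- **Analysis.** Section 10.2 makes each subject their own control for paired pre-post measurements. Section 25.1 says data are "analyzed for differences between baseline and test data", with hypothesis tests. Neither section ties baseline to a visit.
- **Randomisation.** Boost or placebo is allocated at Visit 3, after 30 days in the study lens (section 10.1).

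**The concern.** HydraPEG-coated lenses are first dispensed at Visit 2. Visit 1 therefore holds the only scheduled acuity score in the habitual lens, and it is the natural baseline for any contrast with and without HydraPEG. That score includes whatever spherical error the habitual lens has left uncorrected. The study-lens score comes from a lens ordered with its power updated. The two scores can differ with no surface effect at all.

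Nobody stays in habitual lenses as a control, so nothing in the design separates the parts of the change. At stake is a significant result on a primary endpoint, read as better vision from the coating when part or all of it is a new prescription.

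**Working it through.** **1. What each acuity score contains.** Let *a* be the acuity an eye reaches with its spherical error corrected, *r* the letters lost to residual error in the habitual lens, *s* any surface effect, *o* the effect of a new lens, fit or brand, and *e* measurement error.

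- Visit 1, habitual lens as worn: *a* − *r* + *e*1
- Visit 2 or later, study lens with updated power: *a* + *s* + *o* + *e*2
- Difference: *s* + *r* + *o* + (*e*2 − *e*1)

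The planned comparison cannot separate *s* from *r* + *o*. For an AVT wearer whose parameters are re-ordered unchanged, *r* is in both scores and cancels, so these subjects are less exposed.

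**2. The randomised comparison.** Visits 3, 4 and 5 are all in the study lens. Its power and fit are common to both ends of the change and cancel within each subject, provided that the parameters are not altered. In a simulation with no treatment effect (15 per arm assumed, since no allocation ratio is given; SD 5 letters; rank-sum test at 5%), the Visit 3 to Visit 4 comparison rejected in 4.9% of 4,000 trials.

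**3. Size of the false gain.** The plan has no power calculation, acuity SD or refractive data, so there is no figure of its own to reproduce. From the documents: 30 subjects analysed (section 5.2), and a chart of 14 lines × 5 letters = 70 letters, which is 0.1/5 = 0.02 logMAR per letter. Assumed: a share *f* of subjects gains *g* letters from power alone, the SD of all other change is 4-6 letters, and *s* = *o* = 0. A gain of 3-5 letters is 0.06-0.10 logMAR.

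- Mean false gain = *f* × *g*
- Total SD = √(SD² + *g*² *f* (1 − *f*))
- Noncentrality = mean ÷ (total SD/√30)
- Probability = chance that *t* on 29 degrees of freedom exceeds 2.045, the upper half of a two-sided 5% test (nominal 2.5%)

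At the midpoint: mean = 0.35 × 4 = 1.4 letters. Total SD = √(25 + 16 × 0.35 × 0.65) = √28.64 = 5.35. Standard error = 5.35/√30 = 0.977. Noncentrality = 1.4/0.977 = 1.43. Probability = 28%.

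| Share | Gain (letters) | SD | Mean false gain | Noncentrality | Falsely significant gain |
|---|---|---|---|---|---|
| 20% | 3 | 6 | 0.6 | 0.54 | 7.5% |
| 35% | 4 | 5 | 1.4 | 1.43 | 28% |
| 30% | 5 | 4 | 1.5 | 1.78 | 41% |
| 50% | 5 | 4 | 2.5 | 2.90 | 80% |

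Simulation of the same *t*-test agrees to within one percentage point. The signed-rank test, which is closer to the paired non-parametric analysis in section 10.2, gives about 7-8%, 27%, 37-38% and 77-78% for the four rows.

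**The case against.** The strongest reply is that the trial's goal is whether Boost replenishes the coating. That question is answered from Visit 3, in one lens and against randomised placebo. Section 1.2 expects the effect to show in symptoms and wettability, and the study calls itself a pilot. All of this stands. A reader might infer that the power update confounds the Boost result. It does not, unless a lens is changed after the Visit 3 measurement. The Visit 3 and Visit 4 worksheets do have a place for parameter changes.

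Three other stronger readings also fail:

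- **Refractive drift in the same lens after dispensing might distort later acuity.** Nothing in the documents points to such drift, and Visit 4 is one day after Visit 3. In a randomised comparison it would be noise rather than bias.
- **Acuity is never recorded after an over-refraction.** Visit 1 item 23d does record a final acuity after the diagnostic-lens over-refraction. But it is for scleral wearers only, uses a different lens, and does not say that the over-refraction is in place. It cannot serve as a best-corrected habitual-lens baseline.
- **The 41% row is typical.** It pairs the largest assumed gain with the smallest assumed SD. The midpoint of the ranges gives 28%.

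It is also fair to say that acuity through the over-refraction would not isolate HydraPEG, because lens, fit and often brand change as well. That argues against making it the endpoint at every visit. It does not make the Visit 1 contrast interpretable.

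**Conclusion.** The concern holds for one contrast: habitual lens at Visit 1 against study lens at any later visit. That contrast has no concurrent control, the plan does not rule it out as the baseline comparison, and a gain in it cannot be attributed to the coating.

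The 7-80% range shows what could happen, not what is likely. It rests wholly on the assumed share, gain and SD, and the upper end needs half the subjects to gain five letters. If most subjects already wear AVT lenses re-ordered unchanged, the false gain would be nearer the lower end or below it. The matter is still worth correcting, because acuity is a primary endpoint and the remedy is mostly a matter of wording.

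**What to change.** In sections 9.1, 10.2 and 25.1:

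1. Define the acuity baseline for the Boost question as Visit 3 in the study lens. Make the Boost-versus-placebo difference in change from Visit 3 to Visits 4 and 5 the acuity comparison. Flag eyes whose lens parameters were changed.
2. Report acuity change from Visit 1 to the study lens as descriptive only, and state that it will not be attributed to HydraPEG.
3. State how the over-refraction already recorded will be used to flag, or adjust for, eyes whose power changed.
4. Optionally, add one letter count per eye through the over-refraction at Visits 1 and 2. This is one field and an estimated 1-2 minutes per eye per visit.

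The first three need no new measurement. The price is that the trial makes no formal acuity claim for HydraPEG against habitual lenses. Even with the optional count, residual astigmatism is not removed where the over-refraction is spherical only.
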